5.3.8 Muscle symptom characteristics

We define an outcome that is the difference between the rating (scale = 0,1,2,3) of muscle symptom characteristics during atorvastatin treatment and the rating (scale = 0,1,2,3) of muscle symptom characteristics during placebo treatment for each of the 15 characteristics. The outcomes (differences) have seven possible values: -3, -2, -1, 0, 1, 2, 3. Negative values indicate stronger characteristics on placebo, whereas positive values indicate stronger characteristics on atorvastatin.

5.3.9 Time to symptoms

The number of weeks from start of atorvastatin treatment to confirmed SAMS, as defined in Section 5.1.2, for the patients with confirmed SAMS.

The number of weeks from start of atorvastatin treatment to the week with the highest VAS symptom score (all patients).

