2.7 Timing of Outcome Assessments

For all clinically planned measures, visits should occur within a window of the scheduled visit. Visits outside visit window is regarded a protocol deviation. The target day and visits window are defined in the protocol as:

STATISTICAL ANALYSIS PLAN for MUScle Side-Effects of atorvastatin in coronary patients (MUSE) – a randomized controlled trial

Visit Label	Target Day	Definition (Day window)
Screening	Day -60 to -1	Prior to Day 0
V1. Baseline	Day 0 (Randomization)	Day 0
V2	56**	Target day \pm 2 days
V3	112**	Target day \pm 2 days
Last study visit*	112**	112

*The last study visit is defined as the visit following the last visit with randomised treatment, and where there is a study end statement.

**According to the protocol, V2 and V3 (last visit) may be scheduled after a treatment period of at least three consecutive study weeks (21 days) in participants with intolerable muscle complaints.

For analysis and tabulation purposes, we define study time points as

Time Point Label	Target Day	Definition (Day window)
TP1. Baseline	Day 0 (Randomisation)	Information up to randomisation
TP2. Week 8	56	Days 1 to 56
TP3. Week 16	112	Days 56 to 112

If more than one visit fall into the same time point interval, information on all visits will be used in the analyses.

3 Statistical Principles

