5.1.4 Muscular symptom location

Muscular symptom location is obtained through patient self-report measured with the Brief Pain Inventory at the end of each 7-weeks treatment period. Presence of symptoms (yes/no) are noted on the following locations: neck/shoulder/trunk, proximal upper extremities, proximal lower extremities, distal upper extremities, distal lower extremities and bilateral vs. unilateral.

Detailed differences in muscle symptom location (i.e. «Dermatome pain map» (Margoli Dermatome Pain Map) Margolis RB et. Al. Pain 24:57–65, 1986) will be explored in a separate sub-study publication.

STATISTICAL ANALYSIS PLAN for MUScle Side-Effects of atorvastatin in coronary patients (MUSE) – a randomized controlled trial

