6.1 Carry-Over Effect

The length of each treatment period was chosen on the basis of previous evidence from a large case control study¹⁸ and an observational study¹⁷ suggesting that SAMS appear on median two and four weeks after re-challenge and initiation of statin treatment, respectively. The washout periods equate to more than 10 half-lives of atorvastatin¹⁹ and the primary outcome will be analysed on the basis of symptom intensity in the last three weeks of each treatment period. Because SAMS improve after a median of two weeks following treatment discontinuation¹⁸, we assume that there is no carry-over effect in this trial.

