6.2 Period Effect

Because of the short treatment periods in this trial, it is very unlikely that there will be a trend over time that affects the trial or its patients; thus, we assume that there is no period effect in this trial.

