6.4.9 Time to symptoms

Time to symptoms will be presented with descriptive statistics.

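### Weeks to the highest VAS score is derived on atorvastatin only, so the figure has no reference value and cannot be attributed to the drug

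*SAP*

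**What the plan says.** SAP 5.3.9 defines two measures under one heading. The first is weeks to confirmed SAMS, in patients with confirmed SAMS. The second is "The number of weeks from start of atorvastatin treatment to the week with the highest VAS symptom score (all patients"). Section 6.4.9 covers both with one sentence: "Time to symptoms will be presented with descriptive statistics". No section derives the peak week for the placebo period, and none says which week counts when two or more weeks share the highest score.

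Other parts of the SAP bear on how the figure would behave:

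- Section 5.1.4 gives the period length, through an instrument "measured with the Brief Pain Inventory at the end of each 7-weeks treatment period".
- Section 2.7 lets the end-of-period visit come early: it "may be scheduled after a treatment period of at least three consecutive study weeks (21 days) in participants with intolerable muscle complaints".
- Section 5.1.1 takes diary VAS scores from both periods for the primary outcome, so the placebo scores exist.
- Sections 5.3.7 and 5.3.8, the neighbouring symptom outcomes, are defined as atorvastatin minus placebo.

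**The concern.** A maximum is not an event that a patient may or may not have. Anyone who fills in the diary has a highest week, including a patient whose scores only fluctuate around a constant level. The distribution of that week is therefore set largely by how many weeks are searched, by any drift common to both treatments, by how ties are resolved and by how many periods end early. None of these is an effect of atorvastatin.

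The randomised, blinded placebo period would show what these features produce on their own in the same patients. Without it, a reader who is given a median peak week on atorvastatin has nothing to compare it with. The SAP's introduction stresses nocebo symptoms and cites a blinded crossover study that confirmed SAMS in only 36% of patients with complaints, so many patients in this all-patient measure may have peaks unrelated to the drug.

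**Working it through.** The SAP states no figure for this outcome, so there is none to reproduce. The check asks what the measure gives when the drug does nothing.

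**Inputs.** Seven weeks per period (5.1.4). One score per week is an assumption, taken from the wording of 5.3.9, which compares weeks. For the size of a trial result, n = 68 from 2.3.

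**1. No effect, no trend, exchangeable weeks.** Each week is equally likely to hold the maximum, P(peak in week k) = 1/7.
- Mean = (1 + 2 + … + 7)/7 = 28/7 = 4.0.
- Variance = (7² − 1)/12 = 4, so SD = 2.0.
- P(peak by week 3) = 3/7 = 43% and P(peak by week 4) = 4/7 = 57%, so the median is 4.
- Simulated week-to-week correlation of 0.5 or 0.8 puts more peaks in the first and last weeks, but the distribution stays symmetric and the median stays 4.
- With 68 patients and independent weeks, the sample median is exactly 4 in 71% of simulated trials and between 3 and 5 in over 99%.

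**2. Still no drug effect, other conditions changed.** Assumed weekly SD 1.5 cm; correlation 0.5 except in the last row.

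| Condition | Median peak week |
|---|---|
| Drift −0.1 / +0.1 cm per week | 3 / 5 |
| Drift −0.3 / +0.3 cm per week | 2 / 6 |
| Low scores, floor at 0, whole-cm rounding; ties to first / last week | 3 / 5 |
| 15% / 30% of periods stopped at random after weeks 3 to 6 | 4 / 3 |
| Eight weekly scores instead of seven, independent weeks | 4.5 |

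The no-effect median thus runs from about 2 to 6.

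**3. A real, sustained effect of 1.0 or 2.5 cm** (correlation 0 or 0.5).
- Starting in week 2: median 4, the same as no effect; mean 4.32 to 4.49.
- Starting in week 4: median 5; mean 4.77 to 5.37. A median of 5 also arises with no effect and a drift of +0.1 cm per week.

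**4. What a placebo column adds.** If the placebo mean is 4.0, the mean within-patient difference is 0 with no effect, 4.32 − 4.0 = +0.3 to 4.49 − 4.0 = +0.5 weeks for an effect from week 2, and 4.77 − 4.0 = +0.8 to 5.37 − 4.0 = +1.4 weeks for an effect from week 4. Drift, tie handling and window length that are common to both periods drop out of the comparison. The difference is not the onset time: an effect that starts in week 2 shifts the mean peak by half a week at most, and the median within-patient difference is 0 in most settings.

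**5. Why the contrast should not be split by SAMS class.** The class depends on the last three weeks of each period (1.2.2 and 5.3.1). High late scores on atorvastatin and low late scores on placebo put a patient in the confirmed group. In simulations with no drug effect (assumed mean 4, between-patient SD 2, weekly SD 1.5, correlation 0 to 0.8), patients classed as confirmed had a median peak week of 5 on atorvastatin and 3 on placebo, a mean contrast of about +1.3 to +1.6 weeks. Non-SAMS patients had about −0.3 to −0.5. The split would produce a timing difference by selection alone.

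**The case against.** The outcome is secondary and descriptive. Section 2.4.1 treats every efficacy analysis other than the primary one as supportive or exploratory, and time to symptoms is not among the objectives in 1.2. The SAP plans no test of the peak week and makes no latency claim from it. All of this stands, and it limits the weight of the point.

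A reader might infer that a median of four weeks would be offered as confirming the background in 6.1, which reports that "SAMS appear on median two and four weeks after re-challenge and initiation of statin treatment". The SAP does not draw that link. The four-week figure there is for initiation, whereas the randomised patients have had SAMS on earlier or current atorvastatin (2.1) and fit the two-week re-challenge figure better. Section 6.1 also concerns when symptoms appear, not when they peak.

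A reader might also infer that the atorvastatin figure says nothing about the drug. That is too strong, since an effect starting in week 4 moved the median to 5. The difficulty is that such a shift cannot be told apart from drift, tie handling or truncation.

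The value of 4 is itself conditional. Section 6.2 holds that "it is very unlikely that there will be a trend over time that affects the trial or its patients", but this supports the assumption of no period effect. It does not establish that weekly scores within a period are exchangeable. What survives is that the no-effect value is unknown in advance and the SAP provides nothing to estimate it.

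**Conclusion.** The point holds for the second measure in 5.3.9 only. Defined on atorvastatin alone, the week of the highest VAS score has no reference value. An inert drug gives a median of 4 with seven weekly scores and no trend, and about 2 to 6 under modest drift, ties or early stopping. The simulated range rests on an assumed weekly SD of 1.5 cm, one score per week and early stopping unrelated to symptoms; the SAP gives no figures for these.

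It would be wrong to read this as a fault in the whole of 5.3.9. Time to confirmed SAMS rests on a classification that already compares atorvastatin with placebo. The primary analysis, the confirmed-SAMS proportion and the safety outcomes are untouched. This is a cheap improvement to a descriptive outcome, not a defect that threatens the trial's conclusions.

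**What to change.** In 5.3.9, define the week of the highest VAS score in each period, counted from the start of that period. In 6.4.9, state that:

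- both periods are presented side by side for all patients, with the within-patient difference (atorvastatin minus placebo) and its 95% CI;
- one tie rule applies in both periods, and covers diaries in which every score is zero;
- when a patient ends one period early, the same number of weeks is searched in both periods;
- the contrast is described as a difference in the timing of peak symptoms, not as onset latency;
- the contrast is not presented by SAMS class.

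The cost is one derived variable, two extra table columns and a few sentences. The placebo diary is already collected, so no visit, measurement or patient is added.

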5.3.10 Pharmacogenetics

The presence of the following genetic variables will be determined:

- SLCO1B1: CC genotype vs. CT genotype vs. TT genotype
- CYP3A5: *3/*3 genotype vs. (*1/*3 or *1/*1 genotype)
- CYP3A4: (*1/*22 or *22/*22 genotype) vs. *1/*1 genotype

STATISTICAL ANALYSIS PLAN for MUScle Side-Effects of atorvastatin in coronary patients (MUSE) – a randomized controlled trial

6 Statistical Analysis

6.1 Carry-Over Effect

The length of each treatment period was chosen on the basis of previous evidence from a large case control study¹⁸ and an observational study¹⁷ suggesting that SAMS appear on median two and four weeks after re-challenge and initiation of statin treatment, respectively. The washout periods equate to more than 10 half-lives of atorvastatin¹⁹ and the primary outcome will be analysed on the basis of symptom intensity in the last three weeks of each treatment period. Because SAMS improve after a median of two weeks following treatment discontinuation¹⁸, we assume that there is no carry-over effect in this trial.

6.2 Period Effect

Because of the short treatment periods in this trial, it is very unlikely that there will be a trend over time that affects the trial or its patients; thus, we assume that there is no period effect in this trial.

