2.3 Sample size

Sample size calculations are based on our being able to detect a 1 cm difference in the VAS symptom score between the treatment periods on atorvastatin and placebo since the smallest change in VAS symptom score corresponding to ‘a little more’ or ‘a little less’ symptoms was 1.3 cm, with a lower limit of the CI at 1 cm in a previous study by Gallagher et al¹⁴. Gallagher et al. report a standard

STATISTICAL ANALYSIS PLAN for MUScle Side-Effects of atorvastatin in coronary patients (MUSE) – a randomized controlled trial

deviation (SD) of 1.7 for a difference of 1.0 between two VAS symptom scores. Because of the differences in both populations and specific VAS scale between that study in this one, we use SD=2.5 to account for a much larger variation in this study. With n=68, we will have 90% power to detect a difference of 1.0, using a one-sample T test. With n=68, we will also have 80% power to detect a difference of 40% SAMS under statins vs. 15% SAMS under placebo, using the McNemar test for paired probabilities. To account for some missing information due to drop-outs or and protocol deviations, we plan to include 80 patients.

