2.4.2 Decision Rule

This trial is designed to address a single primary outcome. Higher SAMS under either atorvastatin treatment or placebo treatment is claimed if the primary null hypothesis is rejected at the 5% (alpha = 0.05) significance level (two-sided).

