3.3 Analysis Populations

The Enrolled set will include all patients who have provided informed consent and have been included into the study data base.

The Full Analysis Set (FAS) will be defined as all patients randomly assigned to a treatment group having completed at least three consecutive study weeks on each treatment period.

The Safety Analysis Set will include all patients having received at least one study treatment tablet after randomisation.

The Per Protocol Analysis Set (PPS) will include all randomised patients meeting the study eligibility criteria and with no major protocol deviations affecting the treatment efficacy (i.e. <10% missing data* in the patient diary and >80% tablet adherence in the drug and placebo period, separately), and also being classified as non-adherent to atorvastatin in the end of the placebo study period by direct blood

STATISTICAL ANALYSIS PLAN for MUScle Side-Effects of atorvastatin in coronary patients (MUSE) – a randomized controlled trial

sample measurement according to Kristiansen et al.¹⁵. Patients being classified as partial adherent or non-adherent to atorvastatin therapy in the end of the atorvastatin study period by direct blood sample measurement (Kristiansen et al.¹⁵) will be excluded from the data analyses concerning blood levels of parent drug and metabolites.

**The percentage of missing data for the core self-reported variables in the diary (i.e. the VAS 0-10 cm likert scale and the 0-10 numeric rating scale) will be reported.*

4 Trial Population

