6.3 Primary Outcome

The primary outcome, the difference between the VAS symptom scores for atorvastatin and placebo, will be estimated as the predictive overall margin of a linear regression model with the difference (atorvastatin minus placebo) as the dependent variable and the stratification factors in the randomization (i.e. centre and previous statin discontinuation) as covariates. The estimate and its 95% confidence interval will be presented, with a P-value for the null hypothesis that the difference is zero.

The primary analysis will be performed on the full analysis set. A secondary analysis will be performed on the per protocol set.

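### The primary cross-over model omits randomised sequence, so a period effect would cost precision and, if the sequences are unequal in the FAS, would bias the estimate

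*SAP*

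**What the plan says.** The trial is a two-period AB/BA cross-over with 1:1 randomisation to sequence (SAP 2.1, 2.2). On period, section 6.2 says "we assume that there is no period effect in this trial"; its only reason is the shortness of the treatment periods.

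The primary outcome (6.3) is the atorvastatin-minus-placebo difference in VAS score. It "will be estimated as the predictive overall margin of a linear regression model", with "the stratification factors in the randomization (i.e. centre and previous statin discontinuation) as covariates". Sequence is not a covariate. Section 6.5 checks only whether residuals are normal. Section 6.7 lists two sensitivity analyses, the per protocol set and imputation of a zero difference, and neither concerns period.

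The primary analysis uses the FAS, which is limited to randomised patients "having completed at least three consecutive study weeks on each treatment period" (3.3). The sample size section states: "With n=68, we will have 90% power to detect a difference of 1.0, using a one-sample T test" (2.3).

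**The concern.** A within-patient difference removes stable differences between patients. It does not remove a change that all patients undergo between period 1 and period 2. That change raises the difference in patients who take placebo first and lowers it by the same amount in patients who take atorvastatin first. It cancels only on averaging over equal numbers in the two sequences.

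Short periods do not rule such a change out. The outcome windows are the last three weeks of each period, and with visits at days 56 and 112 they lie about eight weeks apart. Patients enter with ongoing symptoms or a history of stopping because of symptoms (2.1). The outcome is self-reported, and the SAP's own background section describes how expectation can affect such reports. For carry-over, section 6.1 cites sources in support of its assumption; section 6.2 cites none.

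Two things are at stake. The first is precision: drift that the model does not explain goes into the residual variance. The second is bias, if the two sequences are unequal in the FAS. The FAS is fixed after randomisation by completion of three weeks in each period, so blocked randomisation does not guarantee equal numbers in the analysis.

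**Working it through.** **Inputs from the SAP.** Two-sided alpha 0.05 (2.4.2); effect 1.0 cm, SD 2.5, n=68 evaluable, 80 randomised (2.3); blocks of 4 and 6 within centre by previous discontinuation (2.2).

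**Assumption.** Drift p (period 2 minus period 1) is not given in the SAP. It is shown at 0.5, 1.0 and 1.5 cm.

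**1. The plan's own figure.** One-sample t test, noncentral t with 67 df and noncentrality 1.0/(2.5/√68) = 3.30: power 90.16%. The stated 90% reproduces.

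**2. How drift enters.** With treatment effect τ, the expected difference is τ + p in placebo-first patients and τ − p in atorvastatin-first patients. In least squares with an intercept, the overall predictive margin equals the raw mean of the differences. Its expectation is therefore

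τ + p × (n placebo-first − n atorvastatin-first)/n.

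**3. Equal sequences, 34/34, within-sequence SD 2.5.** There is no bias. The model without sequence estimates the residual variance as about 6.25 + p², so

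- interval inflation = √(6.25 + p²)/2.5
- equivalent patients lost = 68 × p²/(6.25 + p²).

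| Drift (cm) | Interval inflation | Patients lost of 68 | Power without sequence | Type I error without sequence |
|---|---|---|---|---|
| 0 | 1.000 | 0 | 90.4% | 5.0% |
| 0.5 | 1.020 | 2.6 | 89.4% | 4.6% |
| 1.0 | 1.077 | 9.4 | 87.3% | 3.6% |
| 1.5 | 1.166 | 18.0 | 83.1% | 2.1% |

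Power and type I error are simulated (40,000 runs per cell, two binary covariates). With sequence in the model, power is 90.1–90.5% throughout. Putting the inflated SD into the ordinary t-test formula would give 89.0%, 85.5% and 79.6%. That overstates the loss: with fixed sequence sizes, drift inflates the estimated standard error but not the true sampling variance of the mean.

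**4. If 2.5 is the total SD.** The within-sequence SD is √(6.25 − p²) = 2.449, 2.291 and 2.000. The planned 90% is kept, and adding sequence would raise power to 91.3%, 94.4% and 98.2%.

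**5. Unequal sequences (placebo-first/atorvastatin-first).** The bias factor is 8/68 = 0.118 at 38/30 and 12/68 = 0.176 at 40/28.

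| Drift (cm) | Bias at 38/30 (cm) | Bias at 40/28 (cm) | Type I error at 40/28 |
|---|---|---|---|
| 0.5 | 0.06 | 0.09 | 5.6% |
| 1.0 | 0.12 | 0.18 | 6.4% |
| 1.5 | 0.18 | 0.26 | 7.8% |

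At 38/30, simulated type I error stays at about 5% or below, because the inflated standard error offsets the bias.

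**6. Adding sequence is not enough unless the margin changes too.** At 38/30, drift 1.0, true effect 1.0, the mean estimates are 1.117 without sequence, 1.117 with sequence and the overall margin, and 1.000 with sequence and the margin at 0. At 40/28, drift 1.0, no true effect, type I error is 6.4%, 8.6% and 4.9% in the same order. The overall margin keeps the bias while the interval narrows around it.

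**7. How likely is imbalance?** At randomisation (n=80, four strata of 20 assumed), the mean absolute difference between sequences is 1.3, and 8 or more occurs in 0.06% of runs. If 12 of 80 (40/40) are then lost at random, a difference of 8 or more has probability about 2.5%, and 12 or more about 0.02%.

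**The case against.** The case for leaving the plan alone is reasonable. The assumption is explicit and pre-specified. With balanced sequences the test is valid and conservative. Systematic bias needs exclusions that depend on sequence, and the SAP gives no reason to expect them. Chance imbalance is ordinary random error: with 12 patients lost at random from 40/40, simulated type I error of a t test without sequence is 4.7% at a drift of 0.5 cm and under 4% at 1.0 and 1.5 cm. A split of 40/28 needs all 12 losses to fall in one sequence, and the allowance of 12 in section 2.3 also covers protocol deviations, many of which remove a patient from the per protocol set and not from the FAS. A drift of 1.0 cm equals the target effect, and 1.5 cm exceeds the 1.3 cm that 2.3 gives for a just noticeable change. Finally, an SD used in a one-sample t test is most naturally the total SD, and 2.3 raised it deliberately ("we use SD=2.5 to account for a much larger variation in this study"), so planned power may not suffer.

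Most of this stands, and it limits the size of the problem. The 40/28 figures are a worst case. At 0.5 cm of drift the cost is an interval 2% wider, about one point of power, and at most 0.09 cm of bias. It does not rescue the model: the assumption is unsupported and unchecked, and dropping it costs almost nothing.

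**Conclusion.** The concern holds. Omitting sequence wastes precision whenever there is a period effect, and it leaves the primary estimate open to bias if FAS exclusions differ by sequence. The likelier consequence is lost efficiency: an interval 2% to 17% too wide for drifts of 0.5 to 1.5 cm at 34/34. Whether this brings power below the planned 90% depends on whether 2.5 is the within-sequence or the total SD. Bias and type I error above 5% need both a real drift and a marked imbalance, which random loss makes rare. All sizes rest on assumed drifts. This should be changed because the remedy is nearly free; it does not by itself invalidate the trial's conclusion.

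**What to change.** In 6.3, add randomised sequence as a covariate, coded +1/2 for placebo-first and −1/2 for atorvastatin-first. Define the treatment effect as the predictive margin with sequence fixed at 0, averaged over the observed values of centre and previous discontinuation, so that both sequences carry equal weight. State that the margin is not averaged over the observed sequence proportions.

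Report half the sequence coefficient, with its 95% CI, as the period difference (period 2 minus period 1), under the no-carry-over assumption of 6.1; the term adjusts for period and neither tests nor corrects carry-over. Use the same model for the per protocol analysis and the zero-difference imputation analysis in 6.7, and say in 6.5 how sequence is handled if median regression replaces linear regression. Remove the reliance on the 6.2 assumption.

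The cost is one covariate and a few sentences. With no drift and equal sequences, the lost degree of freedom takes power from 90.16% to 90.15%. Equal weighting multiplies the interval width by √(n²/(4 × n1 × n2)): √(4624/4560) = 1.007 at 38/30 and √(4624/4480) = 1.016 at 40/28, that is 0.7% and 1.6% wider.
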